12.5.1. Definition of Adverse Events

Adverse Event Definition:

- An AE is any untoward medical occurrence in a participant, temporally associated with the use of a medicinal product, whether or not considered related to the medicinal product.
- NOTE: An AE can therefore be any unfavourable and unintended sign (including an abnormal laboratory finding), symptom, or disease (new or exacerbated) temporally associated with the use of a medicinal product.

Events meeting AE definition include:

- Any abnormal laboratory test results (haematology, clinical chemistry, or urinalysis) or other safety assessments (e.g., ECGs, radiological scans, vital signs measurements), including those that worsen from baseline, and felt to be clinically significant in the medical and scientific judgement of the investigator.
- Exacerbation of a chronic or intermittent pre-existing condition including either an increase in frequency and/or intensity of the condition.
- New conditions detected or diagnosed after study treatment administration even though it may have been present prior to the start of the study.
- Signs, symptoms, or the clinical sequelae of a suspected interaction.
- Signs, symptoms, or the clinical sequelae of a suspected overdose of either study treatment or a concomitant medication (overdose per se will not be reported as an AE/SAE unless this is an intentional overdose taken with possible suicidal/self-harming intent. This should be reported regardless of sequelae).

Events NOT meeting definition of an AE include:

- Any clinically significant abnormal laboratory findings or other abnormal safety assessments which are associated with the underlying disease, unless judged by the investigator to be more severe than expected for the participant's condition.
- The disease/disorder being studied or expected progression, signs, or symptoms of the disease/disorder being studied, unless more severe than expected for the participant's condition.
- Medical or surgical procedure (e.g., endoscopy, appendectomy): the condition that leads to the procedure is an AE.
- Situations where an untoward medical occurrence did not occur (social and/or

convenience admission to a hospital).

- Anticipated day-to-day fluctuations of pre-existing disease(s) or condition(s) present or detected at the start of the study that do not worsen.

12.5.2. Definition of Serious Adverse Events

If an event is not an AE per definition above, then it cannot be an SAE even if serious conditions are met (e.g., hospitalization for signs/symptoms of the disease under study, death due to progression of disease, etc).

Serious Adverse Event (SAE) is defined as any untoward medical occurrence that, at any dose:

a. Results in death

b. Is life-threatening

NOTE:

The term 'life-threatening' in the definition of 'serious' refers to an event in which the participant was at risk of death at the time of the event. It does not refer to an event, which hypothetically might have caused death, if it were more severe.

c. Requires hospitalization or prolongation of existing hospitalization

NOTE:

- In general, hospitalization signifies that the participant has been detained (usually involving at least an overnight stay) at the hospital or emergency ward for observation and/or treatment that would not have been appropriate in the physician's office or out-patient setting. Complications that occur during hospitalization are AEs. If a complication prolongs hospitalization or fulfils any other serious criteria, the event is serious. When in doubt as to whether "hospitalization" occurred or was necessary, the AE should be considered serious.
- Hospitalization for elective treatment of a pre-existing condition that did not worsen from baseline is not considered an AE.

d. Results in disability/incapacity

NOTE:

- The term disability means a substantial disruption of a person's ability to conduct normal life functions.
- This definition is not intended to include experiences of relatively minor medical significance such as uncomplicated headache, nausea, vomiting, diarrhoea, influenza, and accidental trauma (e.g. sprained ankle) which may interfere or prevent everyday life functions but do not constitute a substantial disruption

e. Is a congenital anomaly/birth defect


f. Other situations:
 
 Medical or scientific judgment should be exercised in deciding whether reporting is appropriate in other situations, such as important medical events that may not be immediately life-threatening or result in death or hospitalization but may jeopardise the participant or may require medical or surgical intervention to prevent one of the other outcomes listed in the above definition. These should also be considered serious. Examples of such events are invasive or malignant cancers, intensive treatment in an emergency room or at home for allergic bronchospasm, blood dyscrasias or convulsions that do not result in hospitalization, or development of drug dependency or drug abuse

g. Is associated with liver injury and impaired liver function defined as:
 
 ALT \geq 3xULN and total bilirubin* \geq 2xULN (>35% direct), or ALT \geq 3xULN and INR** $>$ 1.5. 
* Serum bilirubin fractionation should be performed if testing is available; if unavailable, measure urinary bilirubin via dipstick. If fractionation is unavailable and ALT \geq 3xULN and total bilirubin \geq 2xULN, then the event is still to be reported as an SAE.
 
** INR testing not required per protocol and the threshold value does not apply to participants receiving anticoagulants. If INR measurement is obtained, the value is to be recorded on the SAE form.

 Refer to Appendix 2 for the required liver chemistry follow-up instructions

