5.1. Inclusion Criteria

A participant will be eligible for inclusion in this study only if all of the following criteria apply:

AGE

1. Between 18 and 65 years of age inclusive, at the time of signing the informed consent.

TYPE OF PARTICIPANT AND DIAGNOSIS INCLUDING DISEASE SEVERITY
 
2. Blood eosinophils of ≥ 200 cells/μL at screening.
 
3. Asthma: A physician diagnosis of asthma (mild or moderate, as defined by the Global Initiative for Asthma (GINA), 2017) at least 12 months prior to the start of the study. The reason for diagnosis of asthma should be documented in the participant's source data, including relevant history. If available, investigations – specifically evidence of airway hyperresponsiveness, airflow variation (peak flow rate or FEV₁) or reversible airflow obstruction, should also be documented in the participant's source data.
 
NOTE:
 
 • Airway hyper-responsiveness is defined by a methacholine or histamine concentration of <8 mg/mL producing a $\geq 20\%$ fall in FEV₁. • Airflow variation is defined as a variation in peak flow rate (the difference between the highest and lowest peak expiratory flow rate expressed as a percentage of the average peak expiratory flow rate) of $> 20\%$ over a series of measurements or a variation in FEV₁ $> 15\%$ when measured on separate occasions. • Reversible airway obstruction is defined as increase in FEV₁ of $\geq 12\%$ over baseline AND an absolute change of ≥ 200 mL, following 4 inhalations of albuterol/salbutamol inhalation aerosol/spacer (or equivalent nebulised treatment with albuterol/salbutamol solution). 
4. Asthma status: A screening pre-bronchodilator FEV₁ $\geq 60\%$ of predicted normal value.
 
 • NOTE: Predicted values based upon European Respiratory Society guidelines [Quanjer, 2012]. 
5. Asthma control: Asthma Control Test score > 19.
 
6. hsCRP of < 10 mg/L at screening.
 
7. Otherwise healthy (other than the acceptable conditions of asthma and other atopic diseases, including allergic rhinitis and atopic dermatitis) based on a screening medical history, physical examination, vital signs, ECG assessment, pulmonary function testing, and clinical laboratory results.
 
NOTE: A participant with abnormal clinical laboratory parameter(s), which is/are not specifically listed in the inclusion or exclusion criteria, outside the reference range for the population being studied may be included only if the investigator (in consultation with the Medical Monitor) agree and document that the finding is

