5.2. Exclusion Criteria

A participant will not be eligible for inclusion in this study if any of the following criteria apply:

CONCURRENT CONDITIONS/MEDICAL HISTORY (INCLUDES LIVER FUNCTION AND QTc INTERVAL)

1. **Asthma exacerbation:** Any asthma exacerbation requiring systemic corticosteroids within 12 weeks of screening, or that resulted in overnight hospitalization requiring additional treatment for asthma within 6 months prior to screening.
2. **A history of life-threatening asthma.** Defined as an asthma episode that required intubation and/or was associated with hypercapnia, respiratory arrest or hypoxic seizures within the last 5 years.
3. **Significant pulmonary diseases, other than asthma, including (but not limited to):** pneumonia previously requiring hospital admission, pulmonary fibrosis, bronchopulmonary dysplasia, chronic bronchitis, emphysema, chronic obstructive pulmonary disease, or other significant respiratory abnormalities.
4. **Respiratory Infection:** Suspected or confirmed bacterial or viral infection (including tuberculosis) of the upper or lower respiratory tract, sinus or middle ear that occurred within and/or has not resolved within 4 weeks of screening that:
 - led to a change in asthma management
OR
 - in the opinion of the Investigator, is expected to affect the participant's asthma status or the participant's ability to participate in the study.

NOTE: Participants can be rescreened once to allow for an adequate time period between resolution of the infection and randomisation.

5. Positive for **hepatitis B** surface antigen (HBsAg) at screening. (Please refer to [Appendix 8](#) for country specific requirements for Germany)
6. Positive **hepatitis C** antibody test result at screening, or within 3 months prior to first dose of study treatment.

NOTE: Participants with positive Hepatitis C antibody due to prior resolved disease can be enrolled, only if a confirmatory negative Hepatitis C Ribonucleic acid (RNA) Polymerase chain reaction (PCR) test is obtained. Test is optional and participants with negative Hepatitis C antibody test are not required to also undergo Hepatitis C RNA testing.

7. Known **immunodeficiency** (other than that explained by the use of corticosteroids), including a positive test for **HIV** antibody at screening.

8. **Latent or chronic infections** (e.g., genital herpes, urinary tract infections) or at risk of infection (e.g., significant trauma or infection within the 90 days before screening).

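### Does Appendix 5 leave asthma exacerbations after dosing outside the adverse event and serious adverse event data?

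*Protocol*

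**What the plan says.** Section 12.5.1 (Definition of Adverse Events) has four statements that bear on an asthma exacerbation after dosing:

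- Events that are AEs include "Exacerbation of a chronic or intermittent pre-existing condition including either an increase in frequency and/or intensity of the condition".
- Events that are not AEs include "The disease/disorder being studied or expected progression, signs, or symptoms of the disease/disorder being studied, unless more severe than expected" for that participant's condition.
- The note to the general definition extends an AE to any "symptom, or disease (new or exacerbated) temporally associated with the use of a medicinal product".
- Also not AEs are "Anticipated day-to-day fluctuations of pre-existing disease(s) or condition(s) present or detected at the start of the study that do not worsen".

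Section 12.5.2 (Definition of Serious Adverse Events) opens with a condition: SAE status is ruled out for an event that fails the AE definition just given, "even if serious conditions are met (e.g., hospitalization for signs/symptoms of the disease under study, death due to progression of disease, etc". Criterion c then makes an event serious if it "Requires hospitalization or prolongation of existing hospitalization".

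On who is enrolled, Section 5.1 requires "Asthma Control Test score > 19" and controlled disease on stable inhaled therapy. Section 5.2 excludes "Any asthma exacerbation requiring systemic corticosteroids within 12 weeks of screening, or that resulted in overnight hospitalization"; the look-back for the hospitalisation part is 6 months before screening. Section 6.10.1 foresees exacerbations during the study and covers their treatment, but not their classification.

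**The concern.** The AE definition contains two bullets that can both fit the same asthma event and give opposite answers, and nothing says which prevails. The SAE section then offers hospitalisation for the disease under study as its example of a non-SAE, without the severity qualifier that Section 12.5.1 attaches to that exclusion. A site reading the example in isolation might leave an asthma admission out of the SAE data while another site reports it.

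AEs and SAEs are the primary endpoint (Section 3), and asthma exacerbation is not listed as an endpoint elsewhere. The exploratory asthma endpoints are lung function and biomarkers. Under Section 5.5 a single SAE at least possibly related to study drug halts the study. AE definitions act at the point of data capture, so the analysis plan cannot put back an event that was never recorded as an AE.

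**Working it through.** No figure in the protocol measures this point, and no rate of misclassification can be derived from it. The check is a reading of the passages together.

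**Step 1: the scope of the bracketed example.** The example belongs to a sentence whose condition is that the event is not an AE under Section 12.5.1. It illustrates events already screened out there. Section 12.5.1 screens out the studied disease only when it is not more severe than expected. The qualifier therefore applies to the example by reference, although it is not printed again.

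**Step 2: the rest of Section 12.5.2.** Under criterion c, doubt about whether a hospitalisation took place or was needed is resolved towards serious. The other situations to be treated as serious include intensive treatment of allergic bronchospasm, even without admission. Neither fits a reading in which airway events are exempt.

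**Step 3: what is expected in this population.** Participants enter with an ACT score above 19, on stable controller therapy. They have had no steroid-treated exacerbation in the 12 weeks before screening and no overnight asthma hospitalisation needing additional treatment in the 6 months before it. Against that background an admission would ordinarily exceed what is expected.

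**Step 4: three kinds of event.**

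| Event after dosing | Pre-existing-condition bullet | Studied-disease bullet | Result |
|---|---|---|---|
| A. Exacerbation more severe than expected, not serious | AE | AE (qualifier met) | AE |
| B. Asthma admission in a participant with controlled disease | AE | AE (qualifier ordinarily met) | AE, and SAE under criterion c |
| C. Exacerbation judged no more severe than expected | AE | Not an AE | Not settled by the text |

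These rows sort the text; they are not frequencies. A is clear. B is settled once the bracket is read within its own sentence. Only C is open.

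**Step 5: how large C is.** For a participant with controlled asthma, a true exacerbation is by itself a departure from the expected course, so most such events fall in A or B. For what remains, the text gives cues in both directions. The note on exacerbated disease and the restriction of the fluctuation exclusion to conditions that do not worsen favour recording an AE. The studied-disease bullet is the more specific and can be read as qualifying the general one. The choice falls to the investigator.

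**Step 6: what happens if investigators differ over C.** They classify events blind to treatment (Section 6.3), and post-dose eosinophil results are withheld from them (Section 7.3.6). Differences between sites would blur counts, but nothing in the documents suggests they would favour one arm. Safety is summarised descriptively, without formal comparison (Sections 9.1 and 9.4.1). A type C event is by definition the milder kind. It would matter for halting only if it also met a seriousness criterion and was judged at least possibly related.

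**The case for a change.** The best argument for amending is that classification comes before every later safeguard. Causality is assessed for AEs and SAEs, and 24-hour reporting and the SAE halting rule apply to SAEs. An event ruled out at the first step need reach none of them. Section 4.7.1 names bronchospasm among the hypersensitivity reactions of concern, and wheeze is one of the anaphylaxis features in Appendix 9. In an asthmatic such a reaction can look like the underlying disease. With 6 or 9 active participants per cohort and about 6 sites, one event handled differently is visible. The wording also reads like general text not adapted to a trial in which the pre-existing disease is the one studied.

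Part of this stands. The overlap is real, no sentence resolves it, and the example would be clearer with its qualifier printed.

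The rest is weaker. Suspected systemic reactions have their own route: Section 4.7.1 asks investigators to assess them against the anaphylaxis criteria, and Section 5.5 lists possibly related anaphylaxis as a halting criterion in its own right. Exacerbations also leave traces outside the AE form: twice-daily peak flow and rescue use in the diary (Section 7.1), spirometry, coded concomitant medication (Section 8), and changes to maintenance therapy communicated to the sponsor (Section 6.10.1). These do not replace an AE record, but they make an unnoticed loss less likely.

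The obvious remedy is not neutral either. Recording every post-dose exacerbation as an AE would override the severity qualifier that Section 12.5.1 deliberately includes, and the line between exacerbation and expected symptoms would still rest on judgement. The documents support reconciling the two bullets. They do not show which reporting rule is right, and that choice is the sponsor's.

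**Conclusion.** No change to the plan is needed. Followed as written, Appendix 5 makes clear worsenings of asthma AEs and asthma admissions SAEs, because the bracketed example covers only events that Section 12.5.1 has already excluded. What is left is a narrow ambiguity in standard definition wording: an exacerbation judged no worse than expected, in participants selected for controlled disease, classified by a blinded investigator.

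This rests on two assumptions: that sites read the example together with the condition that introduces it, and that an admission in this population would be judged more severe than expected. Both are reasonable on the text, though neither is stated as a rule. If the appendix is reopened for another reason, reconciling the two bullets and repeating the qualifier would be a harmless tidy-up. No effect on the trial's results has been demonstrated.

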12.5.3. Definition of Cardiovascular Events

Cardiovascular Events (CV) Definition:

Investigators will be required to fill out the specific CV event page of the CRF for the following AEs and SAEs:
 
 Myocardial infarction/unstable angina Congestive heart failure Arrhythmias Valvulopathy Pulmonary hypertension Cerebrovascular events/stroke and transient ischemic attack Peripheral arterial thromboembolism Deep venous thrombosis/pulmonary embolism Revascularization

12.5.4. Recording of AEs and SAEs

AEs and SAE Recording:

- When an AE/SAE occurs, it is the responsibility of the investigator to review all documentation (e.g., hospital progress notes, laboratory, and diagnostics reports) relative to the event.
- The investigator will then record all relevant information regarding an AE/SAE in the CRF
- It is **not** acceptable for the investigator to send photocopies of the participant's medical records to GSK in lieu of completion of the GSK, AE/SAE CRF page.
- There may be instances when copies of medical records for certain cases are requested by GSK. In this instance, all participant identifiers, with the exception of the participant number, will be blinded on the copies of the medical records prior to submission of to GSK.
- The investigator will attempt to establish a diagnosis of the event based on signs, symptoms, and/or other clinical information. In such cases, the diagnosis will be documented as the AE/SAE and not the individual signs/symptoms.
- Participant-completed Value Evidence and Outcomes questionnaires and the collection of AE data are independent components of the study.
- Responses to each question in the Value Evidence and Outcomes questionnaire will be treated in accordance with standard scoring and statistical procedures detailed by the scale's developer.
- The use of a single question from a multidimensional health survey to designate a cause-effect relationship to an AE is inappropriate.

12.5.5. Evaluating AEs and SAEs

Assessment of Intensity

The investigator will make an assessment of intensity for each AE and SAE reported during the study and will assign it to one of the following categories:

- Mild: An event that is easily tolerated by the participant, causing minimal discomfort and not interfering with everyday activities.
- Moderate: An event that is sufficiently discomforting to interfere with normal everyday activities
- Severe: An event that prevents normal everyday activities. - an AE that is assessed as severe will not be confused with an SAE. Severity is a category utilised for rating the intensity of an event; and both AEs and SAEs can be assessed as severe.
- An event is defined as 'serious' when it meets at least one of the pre-defined outcomes as described in the definition of an SAE.

Assessment of Causality

- The investigator is obligated to assess the relationship between study treatment and the occurrence of each AE/SAE.
- A "reasonable possibility" is meant to convey that there are facts/evidence or arguments to suggest a causal relationship, rather than a relationship cannot be ruled out.
- The investigator will use clinical judgment to determine the relationship.
- Alternative causes, such as natural history of the underlying diseases, concomitant therapy, other risk factors, and the temporal relationship of the event to the study treatment will be considered and investigated.
- The investigator will also consult the IB and/or Product Information, for marketed products, in the determination of his/her assessment.
- For each AE/SAE the investigator **must** document in the medical notes that he/she has reviewed the AE/SAE and has provided an assessment of causality.
- There may be situations when an SAE has occurred and the investigator has minimal information to include in the initial report to GSK. However, **it is very important that the investigator always make an assessment of causality for every event prior to the initial transmission of the SAE data to GSK.**
- The investigator may change his/her opinion of causality in light of follow-up information, amending the SAE data collection tool accordingly.
- The causality assessment is one of the criteria used when determining regulatory reporting requirements.

Follow-up of AEs and SAEs

- The investigator is obligated to perform or arrange for the conduct of supplemental measurements and/or evaluations as may be indicated or as requested by GSK to elucidate as fully as possible the nature and/or causality of the AE or SAE.
- The investigator is obligated to assist. This may include additional laboratory tests or investigations, histopathological examinations or consultation with other health care professionals.
- If a participant dies during participation in the study or during a recognised follow-up period, the investigator will provide GSK with a copy of any post-mortem findings, including histopathology.
- New or updated information will be recorded in the originally completed CRF.
- The investigator will submit any updated SAE data to GSK within the designated reporting time frames.

